6.3.0 End of Study

Subjects will be instructed to connect to the Keto Mojo App to allow it to sync with the Keto-Mojo Monitor. Once the study is complete, the subject will be instructed to close all browser windows and to dispose of any unused study product (either by flushing down the toilet or pouring down the drain). The sharps container can be mailed using the provided return envelope for disposal.

7 Study Procedures

7.1 Clinical Evaluations

There are no clinical evaluations to be completed as part of this study protocol.

7.2 Laboratory Evaluations

7.2.1 Clinical Laboratory Evaluations: Blood BHB Measurement

To determine blood BHB levels, each participant will be provided with a Keto-Mojo Monitor⁴ (Keto-Mojo, Amsterdam, Netherlands). The monitor allows for each subject to measure their own ketone levels (*i.e.*, BHB levels), through sampling of capillary blood. Moore *et al.* (2021) tested the Keto-Mojo meter for accuracy *versus* the Abbott Lab Precision Xtra glucose/ketone device (Abbott's ketone meter) and reported there was excellent agreement between the two meters. Abbott's ketone meter has been validated in comparison to mass spectrometry (the gold standard of ketone measurement) in animal studies (Pineda and Cardoso, 2015; Bach *et al.*, 2016) and in humans at ketone levels below 3 mM (Janssen *et al.*, 2010; Yu *et al.*, 2011). In their publication, Moore *et al.* (2021) indicate:

“For the purpose of identifying nutritional ketosis, the Keto-Mojo device (Meter 2) is a reliable and accurate portable blood ketone measurement device that is more cost-effective than another commonly used portable ketone meter, the Precision Xtra (Meter 1). The acceptable measurement error, consistent level of agreement, and high diagnostic performance of Meter 2 compared to Meter 1 makes it appropriate for use by recreational or professional athletes interested in verifying that they are in a state of [nutritional ketosis] on a daily basis.”

Capillary blood BHB levels will be measured at baseline (0 min) and at 30, 60, 90, 120, 180, 240, and 300 minutes of the study. A total of 10 fingersticks will be taken [8 study timepoints + 2 control timepoints (maximum)]. A typical blood drop contains ~35 µl of blood⁵. It is likely that 2 to 3 drops, per fingerstick, will be required (*i.e.*, 105 µl of blood). Total blood collection during the study will be: (8+2) X 105 µl = 1,050 µl or 1.050 ml. Frequent fingerstick blood sampling is common when examining post-prandial glycaemic responses, as capillary blood is more ideal (subject to less variability) than venous blood, as per the International Organization for Standardization (ISO 26642:2010⁶). Also, as per this standard, the number of fingerstick blood sampling is 8, which is very similar to the number in our protocol. Although our interest is in post-prandial ketone (BHB) responses, the analogy is relevant with respect to the acceptability of the blood sampling schedule and frequency of blood draws.

⁴ Available at: <https://keto-mojo.com/video/why-keto-mojo-is-the-gold-standard-for-testing-blood-ketones/>.

⁵ Available at: [Not Every Drop of Blood Is Identical | The Partnership for Global Health Technologies \(bu.edu\)](https://www.bu.edu/global-health-technologies/news/2019/05/21/not-every-drop-of-blood-is-identical/)

⁶ Available at: <https://www.iso.org/standard/43633.html>

7.3 Questionnaire Assessments

7.3.1 GI Symptoms Assessment

A validated tool to measure GI tolerability of (R)-1,3-butanediol will be utilized. The mVAS GI symptoms tool is a self-administered questionnaire, which is modelled after the validated “gold standard” measurement tool predominantly used to test clinical gastroenterology scenarios (Bengtsson *et al.*, 2013). Gaskell *et al.* (2019) tested the reliability of the mVAS in assessing GI symptoms during exercise, with and without dietary interventions. The mVAS has been modified slightly for this clinical study protocol, as there is no exercise employed in this study. The mVAS uses a 10-point rating scale to self-report on GI symptoms; 1–4 is indicative of mild GI symptoms (*i.e.*, sensation of GI symptoms, but not substantial enough to interfere normal activities); 5–9 is indicative of severe GI symptoms (*i.e.*, GI symptoms substantial enough to interfere with normal activities), and 10 is indicative of extremely severe GI symptoms warranting cessation of all other activities. If no specific GI symptom is reported, this would be recorded as a 0. A sample of the questionnaire is available within the screen captures of the online portal (**Appendix C**). In the study by Gaskell *et al.* (2019), GI symptoms, such as regurgitation and defecation, were rated dichotomously, either as 0 (no symptom) if they did not result in a cessation of exercise or as 10 (extremely severe symptoms) if they resulted in either a temporary or complete cessation of exercise; in this clinical study, these have been modified to a full 10-point VAS scale. All subjects will complete the mVAS at baseline (0 minutes), and at 30, 60, 90, 120, 180, 240, and 300 minutes.

9.1 Definitions

Unanticipated Problems Involving Risk to Subjects or Others

Any incident, experience, or outcome that meets all of the following criteria:

- Unexpected in nature, severity, or frequency [*i.e.*, not described in study-related documents such as the Institutional Review Board (IRB)-approved protocol or consent form];
- Related or possibly related to participation in the research (*i.e.*, possibly related means there is a reasonable possibility that the incident, experience, or outcome may have been caused by the procedures involved in the research); and
- Suggests that the research places subjects or others at greater risk of harm (including physical, psychological, economic, or social harm).

Serious Adverse Event

AEs are classified as serious or non-serious. A serious adverse event (**SAE**) is any AE that is:

- fatal
- life-threatening
- requires or prolongs hospital stay
- results in persistent or significant disability or incapacity
- a congenital anomaly or birth defect

- an important medical event

Important medical events are those that may not be immediately life-threatening, but are clearly of major clinical significance. They may jeopardize the subject, and may require intervention to prevent one of the other serious outcomes noted above. For example, a seizure that did not result in in-patient hospitalization, or intensive treatment of bronchospasm in an emergency department would typically be considered serious.

All AEs that do not meet any of the criteria for serious should be regarded as **non-serious AEs**.

Adverse Event Reporting Period

The study period during which AEs must be reported is normally defined as the period from the initiation of any study procedures to the end of the study treatment follow-up. For this study, the study treatment follow-up is defined as the evening of the day on which the clinical study takes place.

Pre-existing Condition

A pre-existing condition is one that is present at the start of the study. A pre-existing condition should be recorded as an AE if the frequency, intensity, or the character of the condition worsens during the study period.

General Physical Examination Findings

As the study product is a food ingredient that is GRAS in the U.S., there are no general examinations planned for this clinical study.

Post-study Adverse Event

All unresolved AEs should be followed by the investigator until the events are resolved, the subject is lost to follow-up, or the AE is otherwise explained. While adverse events related to GI intolerance are being solicited, the study participants will also be able to provide information on any other adverse events experienced at the end of the mVAS questionnaire, where space is provided for detailing "other" adverse events, including those that are not GI related.

Hospitalization, Prolonged Hospitalization or Surgery

Any AE that results in hospitalization or prolonged hospitalization should be documented and reported as a SAE unless specifically instructed otherwise in this protocol. Any condition responsible for surgery should be documented as an AE if the condition meets the criteria for an AE.

Neither the condition, hospitalization, prolonged hospitalization, nor surgery are reported as an AE if hospitalization or prolonged hospitalization is for diagnostic or elective surgical procedures for a preexisting condition. Surgery should **not** be reported as an outcome of an AE if the purpose of the surgery was elective or diagnostic and the outcome was uneventful.

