5.1 Description and Treatment Regimen

An outline of the study timepoints is provided in Table 5.1-1. At Screening, subject eligibility will be determined using an online survey (**Appendix A**). Participants will be enrolled in the study in groups of 10 at a time. Participants will eat a meal the night before the study and begin the study the next morning in a fasted state (*i.e.*, overnight, 12-hr fast). The time at which the last meal was consumed and the study start time should be recorded using the online portal (**Appendix C**).

The study will be approximately 300 minutes (5 hours), from start to finish. Completion of study questionnaires, assessment of blood BHB levels, and consumption of the Avela™ beverage will be completed, as per Table 5.1-1; a detailed description of the methodology for each study timepoint is provided in section 6.0 of this clinical study protocol.

Table 5.1-1 Clinical Study Outline

Assessment	Tool Utilized	Screening (up to 7 days prior to test day)	Time (min)								
			0	30	60	90	120	180	240	300	
Eligibility for study participation	On-line Survey	X	-	-	-	-	-	-	-	-	-
GI symptomatology	mVAS GI Symptoms Tool	-	X	X	X	X	X	X	X	X	X
Sleepiness/Alertness Assessment	Stanford Sleepiness Scale	-	X	X	X	X	X	X	X	X	X
Blood BHB levels	Keto-Mojo Monitor	-	X	X	X	X	X	X	X	X	X
(R)-1,3-butanediol consumption	Avela™	-	X	X	X	-	-	-	-	-	-
ALOHA Bar consumption	Not applicable	-	-	-	-	-	-	-	X	-	-

BHB = beta-hydroxybutyrate; GI = gastrointestinal; min = minutes; mVAS = modified visual analogue scale.

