9.2 Recording of Adverse Events

Although AEs are not expected, should any non-serious or serious AEs occur, it is recommended that the participant seek immediate treatment. All AEs occurring during the study period must be recorded. The clinical course of each event should be followed until resolution, stabilization, or until it has been determined that the study treatment or participation is not the cause. SAEs that are still ongoing at the end of the study period must be followed up to determine the final outcome. Any SAE that occurs after the study period and is considered to be possibly related to the study treatment or study participation should be recorded and reported to the IRB immediately.

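### The AE reporting period runs to the evening of the test day, but the last AE collection step in the visible schedule is at 300 minutes, so a late count of zero could not be interpreted

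*Combined protocol and SAP*

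**What the plan says.** All references are to the combined protocol and SAP.

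- **Length of the AE period.** Section 9.1 starts it at the first study procedure and ends it with follow-up. It adds: "For this study, the study treatment follow-up is defined as the evening of the day on which the clinical study takes place". No clock time or interval is given.
- **Duty to record.** Section 9.2: "All AEs occurring during the study period must be recorded".
- **Role of AEs.** Section 3.3 names unsolicited AEs as the primary safety endpoint.
- **Collection.** Section 9.1 says GI intolerance is solicited and that participants can also give "information on any other adverse events experienced at the end of the mVAS questionnaire".
- **Timing of collection.** Section 7.3.1: "All subjects will complete the mVAS at baseline (0 minutes), and at 30, 60, 90, 120, 180, 240, and 300 minutes". Tables 5.1-1 and 6-1, sections 6.2.2 to 6.2.9 and Appendix B agree, and none lists a later step.
- **Session.** Under section 5.1, participants "begin the study the next morning in a fasted state". The same section states: "The study will be approximately 300 minutes (5 hours), from start to finish".
- **Close of session.** Section 6.3.0 has participants sync the meter app, shut the browser and discard unused product. The closing line of Appendix B tells them that they have finished.
- **Later provisions.** Section 9.1: "All unresolved AEs should be followed by the investigator until the events are resolved". Section 9.2 also requires recording and reporting to the IRB of "Any SAE that occurs after the study period and is considered to be possibly related to the study treatment" or to study participation.

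**The concern.** The sponsor chose a reporting period longer than the test session, but the visible schedule has no AE step in its last part. A participant who follows the instructions exactly makes the last entry at 300 minutes and is told that nothing more is due. That message may also discourage anyone from volunteering a later symptom.

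What is at stake is how the safety result can be read. Participants are at home (section 4.2), there is no study monitoring (section 11.1), and publication is planned (section 14). If the report shows no AEs after 300 minutes, a reader cannot know whether none occurred or none was collected. The point concerns new, non-serious events only.

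**Working it through.** **1. The plan's own figure.** Section 5.1 gives 300 minutes as 5 hours: 300 / 60 = 5.0 h. This reproduces.

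**2. Coverage by the last described step.**

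| From | Time (min) | To the last mVAS at 300 min |
|---|---|---|
| First serving (section 3.1) | 0 | 300 - 0 = 300 min |
| Third serving (section 3.1) | 60 | 300 - 60 = 240 min |
| Protein bar, after the 240-min assessments (Table 6-1) | 240 | 300 - 240 = about 60 min |

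**3. Does the period outlast the last step?** The plan gives no clock times. Taking morning to mean before 12:00, the 300-minute step falls before 12:00 + 5 h = 17:00. Any end of the period later than 17:00 therefore leaves an uncovered span, whatever the start time.

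The length of that span is (end of period) - (start) - 5 h. It needs clock times that must be assumed:

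- 10:00 to 18:00: 8 - 5 = 3 h
- 08:00 to 20:00: 12 - 5 = 7 h
- 06:00 to 22:00: 16 - 5 = 11 h

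This range illustrates the span only. It is not an estimate of missed events, and the conclusion does not depend on it.

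**4. Does another visible provision cover the span?**

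| Provision | What it covers | Detects a new non-serious AE after 300 min? |
|---|---|---|
| 9.1, follow-up of unresolved AEs | Events already known | No |
| 9.2, ongoing SAEs at the end of the period | Serious events already known | No |
| 9.2, SAEs after the period | Serious, possibly related events | No |
| 3.1, e-mail to study staff | Questions about the consent form before signing | Not described for AEs |
| 10.2, source documents | Examples are consent forms and portal data | No AE form, call or diary mentioned |
| 12, ethical considerations | Refers injury and sickness policy to the consent form | Cannot be judged; form not visible |

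**5. What a zero would mean.** If all 30 participants answered a closing question and none reported a late AE, the one-sided 95% upper limit for the proportion affected would be 1 - 0.05^(1/30) = 0.095, or 9.5%. This assumes that anyone affected says so when asked. Without such a question, the number of participants observed after 300 minutes is unknown, and the documents support no limit. Section 8 specifies no AE analysis, so the 9.5% corresponds to no planned inference. It only shows why the number of responders is needed.

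**The case against.** **The absence may lie in pages that cannot be seen.** The consent pages were removed and the Appendix C screens are not shown. Section 12 places the policy on injury and sickness in the consent form, so a contact for reports may well be there. This stands. A reader might infer that participants have no means of reporting a late event, but the documents do not support that. They support only the statement that the visible text describes no scheduled step, and no route for volunteered reports, after 300 minutes.

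**Unsolicited AEs are volunteered by definition, so no prompt is needed.** This stands in part. A prompt is not strictly required, but a known route is. Without a count of those asked, a zero also remains uninterpretable.

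**The consequence is small.** Agreed. The BHB endpoint and the GI and sleepiness data to 300 minutes are untouched, and section 9.2 deals separately with ongoing and later related SAEs. A reader might infer that late serious events are ignored or that the safety endpoint is invalid; the text supports neither.

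**A wording change would also remove the mismatch.** Correct. Ending AE ascertainment at 300 minutes would be consistent, at the price of the later hours that the sponsor chose to cover.

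**A late step can bring problems of its own.** A fixed clock time would give early starters longer follow-up than late starters. A repeated mVAS in the evening would add a ninth GI assessment, after uncontrolled eating. Both points stand and shape the fix.

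**Conclusion.** The point holds as a minor inconsistency in safety ascertainment. Sections 9.1 and 9.2 require AEs to be recorded to the evening, while the visible schedule stops collecting them at 300 minutes, 240 minutes after the third serving. New non-serious AEs in between depend on volunteered reports and may be under-captured.

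The conclusion assumes that a morning start means before noon, that the evening ends after 17:00, and that the unseen consent and portal pages add no later prompt. If they give a contact, late events are more likely to be captured, but the number of participants actually asked would still be unknown.

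A reader might want to turn this into a number of missed events. The documents do not allow it, because they give neither clock times nor a rate of unprompted reporting.

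**What to change.** Reconcile sections 5.1, 6.3.0 and 9.1 with the closing message in Appendix B.

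**Preferred.**
- In 9.1, define the end of the AE period in the same way for every participant, for example as a fixed interval after the first serving that is long enough to reach the evening.
- At that point, add one short open portal question on any AE since 300 minutes. The mVAS need not be repeated.
- List the question in Table 5.1-1, section 6.3.0 and Appendix B, and change the 300-minute message so that participants know one entry is still due.
- Keep the answers apart from the 0 to 300 minute GI endpoint.
- Report how many of the 30 answered.

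**Alternative.** State that AE ascertainment ends at 300 minutes and limit the safety conclusion to that window.

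**Cost.** The preferred change takes a few minutes per participant, some reminders to non-responders, and follow-up of any added AEs as section 9.2 requires. AE counts may be higher. The alternative costs only wording, but gives up the late hours.

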Objectives	
Primary:
 
To evaluate the level of production of BHB following the consumption of 3 servings of Avela™, with consumption of each serving separated by 30 minutes and each serving providing 11.5 g of (R)-1,3-butanediol [total intake of 34.5 g of (R)-1,3-butanediol]. 
Secondary:
 
To evaluate the acute effects of 3 servings of Avela™, with consumption of each serving separated by 30 minutes and each serving providing 11.5 g of (R)-1,3-butanediol [i.e., total intake of 34.5 g (R)-1,3-butanediol] on:
GI toleranceSleepiness/alertness
Number of Subjects	N = 30 subjects (males and females)

Main Inclusion and Exclusion Criteria
	
Inclusion Criteria:
 
 • Males and females, 18 to 65 years of age • BMI 18 to <35.0 kg/m², inclusive • Weight ≥ 110 lbs • Subject is judged to be in good health on the basis of medical history • Subject is willing to fast for 12 hours prior to study start • Subject is willing to avoid alcohol and intense physical activity the day prior to and on the day of testing • Subject is capable of giving informed consent and complying with all study procedures/requirements. 
Exclusion Criteria:
 
 • Previous GI disorders (e.g., inflammatory bowel disease, irritable bowel syndrome, history of surgery for weight loss, or gastroparesis) • Gastroenteritis in the 2 weeks preceding the study • Diabetes • Weight <110 lbs • History of alcohol or drug abuse • Previous diagnosis of neurological disorders, depression, or mental illness with psychosis • Unexplained alarm features (i.e., unintentional weight loss >10% body weight in the last 3 months, fevers, or blood in stools) • Use of an antibiotic or any medication impacting gut transit during the 2 weeks before the study • Constipation or diarrhea (defined as, on average, less than 3 stools per week or more than 3 stools per day, respectively) • Allergy to tree nuts • Women who are pregnant or breastfeeding • Persons with medical conditions affecting the pancreas, liver, thyroid, or gall bladder.

Study Product, Dose and Route of Administration
	
Avela™, providing 11.5 g of (R)-1,3-butanediol per serving, 3 servings during the test day, with consumption of each separated by 30 minutes, for a total intake of 34.5 g (R)-1,3-butanediol.

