Across both studies, there were no significant differences between the 1,3-butanediol and placebo phases on the time to complete the time trial, and the magnitudes of the effect sizes observed were interpreted as “unclear”. Similarly, no significant differences between phases were observed for power output (Shaw *et al.*, 2019) and pacing (Scott *et al.*, 2019) during the time trial; the magnitudes of the effects were interpreted as “unclear” or “very likely trivial” (for pacing for the first 3-km of the 5-km time trial). Thus, the consumption of 1,3-butanediol compared to placebo did not result in statistically significant or clinically significant improvements in time trial performance. Additionally, the consumption of 1,3-butanediol compared to placebo significantly increased blood BHB levels throughout exercise. However, the consumption of 1,3-butanediol compared to placebo did not result in statistically or clinically significant, sustained improvements in supportive outcomes of exercise performance. Furthermore, the evidence to support an effect of 1,3-butanediol on the sparing of glucose reserves is unclear. It should be noted that, in the study by Scott *et al.* (2019), BHB was elevated following administration of 1,3-butanediol but was not sufficient to induce moderate or high levels of ketosis.

In the study by Shaw *et al.* (2019), there was no difference in the change of body mass (corrected for fluid intake) between trials. Within the group consuming butanediol, two participants experienced low levels of nausea, euphoria, dizziness. Five participants reported low to moderate levels of belching and burping, and one participant reported severe abdominal pain. All participants reported that they disliked the taste of butanediol, which resulted in retching in four participants. In the study by Scott *et al.* (2019), no adverse GI effects were reported.

It should be noted that, in the study by Shaw *et al.* (2019), a pilot test was conducted prior to the primary study to determine a testing dose of 1,3-butanediol in a beverage that was well tolerated and would provide optimal BHB blood concentration. In the pilot test, single bolus doses of 0.5 g/kg and 0.7 g/kg of 1,3-butanediol resulted in nausea, euphoria, and dizziness. To resolve these issues, the authors determined a split dose of 0.35 g/kg (providing about 24.5 g/dose for a 70-kg individual) at the initiation of

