1.5 Conclusions

Avela™ (R)-1,3-butanediol is GRAS for use in beverages, bars, and gels at a level of up to 11.5 g/serving and for 1 to 3 servings per day, yielding total intakes ranging from 11.5 to 34.5 g (R)-1,3-butanediol/day (equivalent to 0.16 to 0.49 g/kg body weight/day). In the clinical trial described herein, study participants will consume a beverage 3 times during the test day, with each serving providing 11.5 g of (R)-1,3-butanediol, for a total (R)-1,3-butanediol intake of 34.5 g on the test day; thus, use of (R)-1,3-butanediol in the clinical trial described herein is within the parameters of the GRAS uses and use levels.

Studies in humans demonstrated no significant adverse effects when 1,3-butanediol provided up to 10% of energy intake for 5 days (Tobin *et al.*, 1975). More recent studies reported that 3 doses up to 35 g/day (Scott *et al.*, 2019) and split-dosing up to 49 g/day (Shaw *et al.*, 2019) of (R, S)-1,3-butanediol (racemic mixture) were well-tolerated by healthy athletes. Consumption of a single bolus dose of 35 or 49 g “tended to result in nausea, euphoria, and dizziness” (Shaw *et al.*, 2019), suggesting that a dosing regimen involving 2 or 3 doses may mitigate the potential GI effects that were observed with consumption of 1 single bolus dose of (R, S)-1,3-butanediol.

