1.6 Dose Rationale and Risk/Benefits

The study dose was chosen based on the level of (R)-1,3-butanediol that was determined to be GRAS for use. Thus, during the test day, study participants will consume 3 servings of Avela™; each serving will provide 11.5 g of (R)-1,3-butanediol. Effects on ketone (BHB) production, GI tolerance, and sleepiness/alertness will be assessed.

2 Study Objectives

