4.2 Total Number of Subjects and Sites

The proposed clinical study is being conducted by Genomatica. Thirty Genomatica employees (males and females) are being recruited for the study. There is no sample size calculation, as there is no control group and the study is a pilot study, with the main objective of understanding ketone (BHB) levels following consumption of (R)-1,3-butanediol. 30 participants are to be included, due to the inherent

variability in the GI symptomology questionnaires. Of note, in other studies of food ingredients (e.g., inulin¹, sorbitol², erythritol + fructose³) where GI tolerance was an outcome of interest, sample sizes ranged from 26 to 37 participants

Genomatica employees who express interest in participating in the study and who meet the eligibility criteria for study inclusion will complete the study remotely, within their own homes, using equipment provided by Genomatica (i.e., lancets, sharps container, alcohol swabs, Keto Mojo BHB monitor and ketone test strips (and glucose test strips, not to be used in the study), bandages, pregnancy test [if applicable], measuring tape, three 4 oz. (118 mL) bottles of sealed water premixed with Avela™ [each providing 11.5 g of (*R*)-1,3-butanediol], 1 shot glass with the Avela™ logo, an ALOHA Organic Plant Based Protein Bar (Caramel Sea Salt), 1 duffel bag, 1 consent form, and study instructions. All study-related data will be entered and transmitted by each study participant using an electronic platform, using surveys that will protect the identity of each participant.

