5.2 Method for Assigning Subjects to Treatment Groups

All subjects included in the study will be assigned to receive the active investigational product [Avela™ (R)-1,3-butanediol] (*i.e.*, there is only one group for the study, with a before, after study design). Upon enrolment, each participant will be provided with a unique identification number.

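### Euphoria and dizziness, which the protocol itself cites as effects of 1,3-butanediol, are left to volunteered comments in the visible text, so their incidence cannot be reliably estimated or excluded

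*Combined protocol and SAP*

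**What the plan says.** Section 1.4 describes the pilot test of the cited cycling study, in which "single bolus doses of 0.5 g/kg and 0.7 g/kg of 1,3-butanediol resulted in nausea, euphoria, and dizziness". In the main part of that study, on divided doses, "two participants experienced low levels of nausea, euphoria, dizziness". Section 1.5 repeats the bolus effects and concludes that 2 or 3 doses "may mitigate the potential GI effects that were observed with consumption of 1 single bolus dose".

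On what this trial will measure, Section 1.6 says "Effects on ketone (BHB) production, GI tolerance, and sleepiness/alertness will be assessed". Sections 2.2 and 3.2.2, Tables 5.1-1 and 6-1, and the participant instructions in Appendix B name the same assessments: blood BHB, the mVAS for GI symptoms and the Stanford Sleepiness Scale (SSS).

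Section 9.1 says that GI intolerance is solicited, and adds that "study participants will also be able to provide information on any other adverse events experienced at the end of the mVAS questionnaire", in a space for other events that may be non-GI. Section 3.3 makes unsolicited adverse events the primary safety endpoint. Section 7.3.1 schedules the mVAS at 0, 30, 60, 90, 120, 180, 240 and 300 minutes. Section 9.2 requires all adverse events in the study period to be recorded. The mVAS item list stands only in Appendix C, whose screen captures are not shown.

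**The concern.** Two of the three effects that Section 1.4 names, euphoria and dizziness, are not GI symptoms. Once Section 1.5 has put them under a GI label, they appear in no objective, endpoint or scheduled assessment in the visible text. Nausea belongs with GI symptoms, so the gap concerns only the other two.

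The SSS does not fill it. Section 7.3.2 describes a single scale from alert to near sleep, with no place for feeling dizzy or euphoric.

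Little else would pick these effects up. Participants are at home (Section 4.2), there are no clinical evaluations (Section 7.1) and no study monitoring (Section 11.1). At stake is how a small count is read: a report of few or no such events could be taken as evidence of tolerability when participants were not asked about them.

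**Working it through.** The plan has no figure to reproduce: "There is no sample size calculation, as there is no control group and the study is a pilot study". The check asks what 30 participants can say about a non-GI effect, with and without a direct question.

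**Inputs**
- n = 30 (Study Summary: "N = 30 subjects (males and females"), in one group without a control (Section 5.2: "there is only one group for the study, with a before, after study design").
- The earlier experience is 2 participants out of 9 on divided doses (Section 1.4), or 22%, with an exact 95% interval of 2.8% to 60.0%. It serves only as an illustrative rate.
- s is the share of affected participants whose event is recorded. The documents give no value. I assume s = 1 for a fixed item and 0.25 to 0.75 for free text.
- p is the true incidence. I assume 5%, 10% and 2/9 for illustration.

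**Formulas**
- Chance of at least one report: 1 - (1 - p·s)^30.
- One-sided 95% upper bound on the true rate after no reports: [1 - 0.05^(1/30)] / s = 0.0950 / s.

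**Results**

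| s | Upper bound after 0 of 30 | At least one report, p = 5% | p = 10% | p = 2/9 |
|---|---|---|---|---|
| 1 | 9.5% | 78.5% | 95.8% | 99.95% |
| 0.75 | 12.7% | 68.2% | 90.4% | 99.6% |
| 0.5 | 19.0% | 53.2% | 78.5% | 97.1% |
| 0.25 | 38.0% | 31.4% | 53.2% | 82.0% |

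**Reading the table**
- If the effects were as common as 2/9, at least one report is likely under every assumed s (82% or more). The free-text space can show that such events occur.
- The rate itself is not recoverable. At s = 0.5, a true 22% would appear as about 11% (0.222 × 0.5). Since s is unknown, the count cannot be corrected.
- Silence is weak evidence. At a true 10%, the chance of no report is 4.2% when everyone is asked (0.90^30) and 46.8% at s = 0.25 (0.975^30).

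**Are these effects relevant at this intake?** The total of 34.5 g is 34.5/70 = 0.49 g/kg at 70 kg. At the 110 lb minimum weight in Section 4.3 (49.9 kg) it is 34.5/49.9 = 0.69 g/kg. It is taken as three servings at 0, 30 and 60 minutes. As a total, this is close to or within the 0.5 to 0.7 g/kg given as single boluses in Section 1.4. Because the servings are divided, this shows that the effects are worth measuring, not how often to expect them.

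**The case against.** The strongest reply is that the plan already has a route for these events. The mVAS, with its space for other events, is completed eight times; unsolicited adverse events are the primary safety endpoint; and all adverse events must be recorded. This stands. A reader might infer that the design cannot show whether euphoria or dizziness occurs at all, and the documents do not support that.

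The item list in Appendix C is also not visible. Section 9.1 shows that GI events are the solicited category, but not which items are listed. If dizziness is among them, the point shrinks to euphoria.

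Three further inferences are tempting and should not be drawn:
- *That dosing was split to avoid these effects.* Section 1.6 bases the dose on the GRAS use level, which Section 1.3 caps at 11.5 g per serving, so 34.5 g needs three servings in any case. Section 1.5 only suggests that dividing doses may help. No objective compares divided with bolus dosing.
- *That the SSS is biased in the product's favour.* Nothing in the documents shows how a euphoric or dizzy person would score, and dizziness could as easily raise the score.
- *That about 7 of 30 would be affected (2/9 × 30 = 6.7).* The 2 of 9 were trained male cyclists, exercising, on the (R,S) form and a different dosing schedule, and the text does not say that each had euphoria or dizziness.

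Finally, prompting in an open-label, uncontrolled study invites some suggestion, and added items would not establish causation. That is a fair limit on what the items can show, but it does not make an unprompted count more informative about incidence.

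**Conclusion.** The point holds in a limited form. The protocol knows of euphoria and dizziness, under bolus and divided dosing, yet in the visible text it leaves both to unsolicited free text. Such events can be recorded, but their incidence cannot be reliably estimated or excluded, and few or no reports would not show absence.

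The size depends on an unknown capture share. No report in 30 excludes rates above 9.5% if every case is captured, about 19% at an assumed 50%, and 12.7% to 38.0% over the assumed range of 75% to 25%. The 9.5% also assumes that a direct question finds every case. The conclusion is conditional on Appendix C: any item already there removes that part of the gap. The BHB objective is not affected. This is an inexpensive improvement to the tolerability assessment, not a flaw that undermines the trial.

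**What to change.** Unless Appendix C already contains them, add two fixed items to the portal, dizziness/light-headedness and euphoria/feeling intoxicated. Score them 0-10 like the mVAS, at all eight existing timepoints including baseline. Report them descriptively as solicited tolerability events, with change from baseline; they need not become secondary endpoints. In Section 1.5, describe the bolus effects as GI and central nervous system effects.

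If the items are not added, the plan should say that the incidence of these effects will not be estimated and that an absence of reports will not be read as an absence of effect.

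The cost is two more questions on an existing online form at eight timepoints, with no added staff or procedure. The downside is some increase in mild reports because participants are prompted in an open-label study without a control. The baseline score helps to interpret them by separating anything already present after the overnight fast.
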